7.1.2.2 Dose-response (Dose vs PD AUC)

The average of pAkt inhibition over the dosing interval (12h) at each dose level will also be estimated from an E_{max} dose-response model accounting for intra-individual correlation for the measurements at different doses.

In the E_{max} dose response model the Hill parameter is fixed to 1 and the inhibition at dose 0 is fixed to 0. The following model will be used:

$$Y_{ij} = \left(\frac{E_{max} \cdot D_{ij}}{ED_{50} + D_{ij}} \right) + e_{ij}$$

Y_{ij} : average pAkt inhibition of the i -th patient on dose $j=1,2,3$

D_{ij} : Dose (mg) of the i -th patient on dose $j=1,2,3$

E_{max} : Maximum effect, logit transformed (between 0 and 100) = $100 / (1+\exp(-\Theta_1))$

ED_{50} : Dose (mg) at which 50% of E_{max} is reached, log transformed $\exp(\Theta_2)$

e_{ij} : residual error normally distributed.

A random effect with normal distribution on transformed parameter Θ_2 will be estimated for each patient to account for the within-subject correlation between time points.

The dose D_{xx} (mg) that provides a given level (xx % of E_{max}) of time-averaged pathway inhibition over a dosing period (12h) is defined as

$$\left(\frac{XX}{100 - XX} \right) \times ED_{50}$$

where ED_{50} the dose at which 50% of E_{max} is reached.

Comercially Confidential Information

Commercially Confidential Information

In case the above model cannot be fitted, a slope model will be fitted:

$$Y_{ij} = \beta D_{ij} + \eta_i + e_{ij}$$

Y_{ij} : average pAkt inhibition of the i -th patient on dose $j=1,2,3$

D_{ij} : Dose (mg) of the i -th patient on dose $j=1,2,3$

η_i : patient effect

e_{ij} : residual error normally distributed.

Depending on the feasibility to measure average baseline unstimulated pAkt levels, the minimum average level of inhibition needed for undetectable pAkt may be determined. If the dose achieving this level of inhibition cannot be estimated reliably from the unstimulated pAkt levels, then the stimulated pAkt levels may be used for the selection of the dose to be carried into Part II. The dose selected for Part II may be different (up to 70 mg bid) than the 3 doses studied in Part I. Other variables may also be taken into account for the selection of the dose.

7.1.3 Handling of missing values/censoring/discontinuations

In Part I, the primary analysis model will include all available data, there will be no imputation of missing data.

7.2 Analysis of secondary and exploratory variables

7.2.1 Efficacy / Pharmacodynamic

The changes from baseline of SF-36 and WPAI-CIQ scores, and of Visual analogue scale scores for PGA and PtGA, will be calculated and summary statistics will be provided by treatment and visit.

Summary statistics by treatment and visit will be provided for the change from baseline in High Sensitivity C-reactive protein (hsCRP) and Lactate dehydrogenase (LDH).

7.2.2 Efficacy: Imaging

The MRI/CT images will be analyzed by VirtualScopics as described in the imaging charter. The following quantitative and qualitative measurements are to be summarized by Covance.

- Sum of product of diameters of the index lesions and percent change in sum of product of diameters relative to baseline
- 3D volume of index lesions.
- Overall index lesion response
- Overall non-index lesion response
- Presence of newly appearing lesions,
- Liver volume
- Spleen volume
- Qualitative assessment of splenomegaly and hepatomegaly
- Overall patient response

The sum of the products of diameters (SPD) of index lesions will be log10 transformed and the change from baseline of the log transformed SPD after 12 weeks of treatment will be calculated for all patients with measureable lymph nodes at baseline. The sum of the 3D volumes of the index lesions will be log10 transformed and the change from baseline after 12 weeks of treatment will be calculated. Spaghetti plots and summary

statistics for the change from baseline of the log10 transformed SPD will be provided. Response (CR [complete response], PR [partial response], etc.) of index and non-index lesions will be analyzed qualitatively. Liver and spleen volumes will be visualized as spaghetti plots.

8 Statistical methods for safety and tolerability data

Boxplots to visualize trends in longitudinal safety data (vital signs, ECG, lab parameters) will be created.

8.1 Patient demographics and other baseline characteristics

All data for background and demographic variables will be listed by age group and patient. Summary statistics will be provided for patients overall.

Relevant medical history, current medical conditions, results of laboratory screens, drug tests and any other relevant information will be listed by patient.

8.2 Treatments (study drug, rescue medication, other concomitant therapies, compliance)

Data for study drug administration (rescue medication) and concomitant therapies will be listed by age group and patient.

8.3 Vital signs

All vital signs data will be listed by age group, patient and visit/time and if ranges are available abnormalities (and relevant orthostatic changes) will be flagged. Summary statistics will be provided by visit/time.

8.4 ECG evaluations

All ECG data will be listed by age group, patient and visit/time, abnormalities will be flagged. Summary statistics will be provided by treatment and visit/time.

8.5 Clinical laboratory evaluations

All laboratory data will be listed by age group, patient and visit/time and if ranges are available abnormalities will be flagged. Summary statistics will be provided by visit/time.

8.6 Adverse events

All information obtained on adverse events will be displayed by treatment and patient.

The number and percentage of patients with adverse events will be tabulated by body system and preferred term with a breakdown by treatment. An adverse event starting in one 'period' (i.e. under one dose level in Part 1) and continuing into the next period is counted only in the onset period. A patient with multiple adverse events within a body system and treatment period is only counted once towards the total of this body system.

Commercially Confidential Information

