1.2 Data from Study Part I

Six APDS/PASLI patients completed study Part I of the present protocol (amendment #8). CDZ173 was found safe and well tolerated at all three dose levels. There were no SAEs and no premature treatment discontinuations due to AEs. In summary, 12 week treatment with CDZ173 led to significant improvements in the clinical presentation of the patients, including regression of lymph nodes and decrease in spleen size, naïve B cell numbers normalization, decrease of elevated transitional B cell numbers, reduction of senescent CD4+ and CD8+ T cells, reduction of elevated serum chemokines and suppression of the PI3K/Akt pathway activity. Mean oral plasma clearance at steady-state in the APDS patients was found to be 3.8 L/h, a value in close agreement to that seen in healthy volunteers. Also, no relevant time-dependencies or deviations from dose-proportionality were evident.

For further details of results please refer to the Clinical Study Report.

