Efficacy, safety and PK assessments will be performed at scheduled times. Safety assessment will include physical examination, ECGs, vital signs, standard clinical laboratory evaluations (hematology, blood chemistry, urinalysis), adverse event and serious adverse event monitoring.

Commercially Confidential Information

Follow-Up/End of study visit

For the patients who do not directly roll over from Part II to treatment in the extension study (CCDZ173X2201E1) at the Part II End of treatment visit, the following applies:

During the four weeks after the last day of dosing the patients will be followed-up for safety. On Day 112 patients will undergo the end of study visit.

Premature discontinuation of study treatment

Patients who discontinue study treatment prematurely will perform an early treatment discontinuation visit (named V104.1) with the assessments marked with a * in the assessment schedule (including imaging), as soon as possible after their treatment discontinuation.

If the premature discontinuation from study treatment happens before the scheduled V104, the patients will be asked to also return at Day 85, and complete the Visit 105 (without further imaging assessments to avoid additional radiation). This will be considered their last Visit.

If on the other hand the premature discontinuation from study treatment happens at or after the scheduled V104, the patients will in addition to the early treatment discontinuation visit be asked to perform the EOS visit 4 weeks after the treatment discontinuation visit. This will be considered their last Visit.

Rationale of study design

The design of this study addresses the primary objective of decreasing lymphoproliferation and its sequelae in patients with APDS/PASLI and takes into account the rarity of this disease.

Commercially Confidential Information

After completion of Part I, the dose selection for Part II was based on the safety and tolerability profile observed during up-titration in Part I (and also in the FIH study), and on a combined assessment of all available

PK/PD and biomarker data. This included PD biomarkers immediately downstream of PI3K δ (notably *ex vivo* stimulated and non-stimulated cellular pAkt levels) as well as biomarkers further downstream (such as cytokine serum levels) to ensure that the selected dose for Part II adequately suppresses the genetically activated pathway.

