Due to the seriousness of the disease and its early onset, adolescent APDS patients already have a long history of hospital visits, including those with invasive measures (e.g. IVIG). Although the additional burden of this clinical trial is relatively modest, procedures, pain and burden will be minimized in adolescents. In particular there will be pain prevention (e.g. by local anesthesia if wished by the participant) and timing coordinated with daily activities as far as possible and defined in the protocol.

MRI or CT scans have associated risks related to the contrast media such as nausea, hypersensitivity reactions, accumulation and functional impact of contrast agents in several organs. In case of known hypersensitivity, no contrast media will be used. Burdens may include discomfort, claustrophobia, fear, pain from venipuncture and heat sensation in case of contrast agent injection and need for specialist setting. Patients will be fully informed about all details of the procedure. During the procedure patients carry an emergency button with them, allowing premature termination of the procedure at any time.

Commercially Confidential Information

Commercially Confidential Information

4 Population

A total of 6 patients with APDS/PASLI were enrolled in the study in Part I. In Part II of the study approximately 30 patients will be randomized. Patients enrolled in Part I of the study will not participate in Part II, i.e. new patients will be recruited.

The Investigator must ensure that all patients being considered for the study meet the following eligibility criteria.

Patient selection is to be established by checking through all eligibility criteria at screening. A relevant record (e.g. checklist) of the eligibility criteria must be stored with the source documentation at the study site.

Deviation from any entry criterion excludes a patient from enrollment into the study.

The inclusion and exclusion criteria listed in [Section 4.1](#) and [Section 4.2](#) are valid for the population to be included in Part I and Part II of the study, no additional differentiation should be made between patients selected for Part I or II.

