- no action taken (i.e. further observation only)
- study treatment dosage adjusted/temporarily interrupted
- study treatment permanently discontinued due to this adverse event
- concomitant medication given
- non-drug therapy given
- subject hospitalized/subject's hospitalization prolonged

6. its outcome (not recovered/not resolved; recovered/resolved; recovering/resolving, recovered/resolved with sequelae; fatal; or unknown)

Once an adverse event is detected, it should be followed until its resolution or until it is judged to be permanent, and assessment should be made at each visit (or more frequently, if necessary) of any changes in severity, the suspected relationship to the study drug, the interventions required to treat it, and the outcome.

Information about common side effects already known about the investigational drug can be found in the Investigator Brochure (IB) or Core Data Sheet (for marketed drugs) or will be communicated between IB updates in the form of Investigator Notifications. This information will be included in the patient informed consent and should be discussed with the patient during the study as needed.

The Investigator should also instruct each patient to report any new adverse event (beyond the protocol observation period) that the patient, or the patient's personal physician, believes might reasonably be related to study treatment. This information should be recorded in the Investigator's source documents; however, if the AE meets the criteria of an SAE, it must be reported to Novartis.

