The change from baseline in naïve B cells out of total B cells at the end of treatment (i.e. the Day 85 assessment for patients who complete the 12 week treatment period or the treatment discontinuation visit for patients who discontinue treatment prematurely prior to Day 85 visit) will be calculated for patients with baseline and end of treatment measurements. Baseline will be defined as the arithmetic mean of the baseline and Day 1 values. An analysis of covariance will be done to compare the change from baseline in the naïve B cells between the two treatment groups, adjusted for baseline naïve B cells count. The use of glucocorticoids and intravenous IgG at baseline will both be included as categorical (Yes/No) fixed effects. Comparison of the two treatment groups will be two-sided, with a 5% type I error. Only patients with a reduced percentage of naïve B cells at baseline (defined as below 48 % [van Gent et al 2009](#)) will be included to the analysis.

In Part I, all vital signs, ECG, and laboratory data were listed by patient and visit/time and if ranges are available abnormalities (and relevant orthostatic changes) were flagged. Summary statistics were provided by visit/time. All information obtained on adverse events was displayed by treatment and patient. The number and percentage of subjects with adverse events were tabulated by body system and preferred term with a breakdown by treatment. An adverse event starting in one period and continuing into the next period was counted only in the onset period. A patient with multiple adverse events within a body system and treatment period was only counted once towards the total of this body system and treatment.

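### Part I counts a continuing adverse event only at the dose where it began, so an event that worsens after escalation can be missing from the higher dose's row

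*SAP*

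**What the plan says.** Part I SAP section 8.6 plans a table of patients with adverse events, "tabulated by body system and preferred term with a breakdown by treatment". Treatment here means dose level, because the same section explains a period as the time under one dose level. An event that starts at one level and is "continuing into the next period is counted only in the onset period". Protocol 11.4.2 repeats the rule: "An adverse event starting in one period and continuing into the next period was counted only in the onset period".

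Three other passages bear on how the rule works.

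- SAP 8.6 also plans a full display: "All information obtained on adverse events will be displayed by treatment and patient".
- Protocol 9.1 follows each detected event to its end, and "assessment should be made at each visit (or more frequently, if necessary) of any changes in severity".
- Protocol 3.1.2, in the rationale of the design, says the Part II dose was chosen partly "based on the safety and tolerability profile observed during up-titration in Part I". Protocol 1.2 then concludes that "CDZ173 was found safe and well tolerated at all three dose levels".

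The unredacted text has no rule for an event that worsens across dose levels and no table of severity by dose level. Redacted text follows the counting rule in SAP 8.6. SAP 1.1 places the table shells and derivation specifications in Modules 7 and 8, which are not among the documents reviewed.

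**The concern.** Counting by onset is an ordinary way to avoid listing one continuing event several times. It suits an event that persists unchanged. It fits less well when the question is whether tolerability changes as the dose rises, because a rise in grade after escalation is then the information of interest.

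In Part I the dose only goes up and the same patients pass through every level. For a single-record event that worsens, the rule can therefore only assign it to a lower dose than the one at which it worsened. Safety and tolerability is a primary Part I objective (Protocol 2.1, Part I SAP 2.1.1.1), and the by-dose table is the natural summary behind a statement about each of the three levels. A reader who relied on that table alone could see no event at 70 mg where a patient's event had in fact become worse.

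**Working it through.** The documents give no figure on how events are attributed to doses, so there is none to reproduce. The check sets the rule against the design and then sizes its possible effect.

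**Inputs**

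- Patients: "A total of 6 patients with APDS/PASLI were enrolled in the study in Part I" (Protocol, section 4 Population). Protocol 3.2.2 says all six completed the 12 weeks, so the denominator is 6 at each level.
- Sequence: 10, 30, then 70 mg b.i.d., four weeks each, in the same patients (Part I SAP 2.2.1).
- Boundaries: Protocol Table 8-1 has visits on Days 28 and 29 and on Days 56 and 57, so the periods adjoin with no gap.
- Counting: onset period only (SAP 8.6, Protocol 11.4.2).

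**Step 1: one record or several?** The effect depends on how a worsening event is stored. Protocol 9.1 asks for a grade and one start and end date per event, and treats a change in severity as something to follow within the event. That favours one record. It is not stated as a rule, however, and the Part II SAP (section 7.2) handles consecutive records under one preferred term, so split records are possible.

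- One record with its original start date: counted at the onset dose only.
- A new record at the grade change: the new record starts in the later period and is counted there, so the problem disappears for that event.

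**Step 2: size under the one-record case.** Let k be the number of patients whose event begins at 10 mg and worsens at 70 mg. Take a preferred term with no other onset at 70 mg. The value of k is assumed; the documents do not give it.

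- Onset rule: 70 mg incidence = 0/6.
- Counting the worsening where it happens: 70 mg incidence = k/6.
- Difference = k/6, or 1/6 = 16.7 percentage points per patient.

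The exact (Clopper-Pearson) 95% limits are the 2.5% point of Beta(k, 7 − k), taken as 0 when k = 0, and the 97.5% point of Beta(k + 1, 6 − k).

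| k (assumed) | 70 mg, onset rule | 70 mg, worsening counted | Exact 95% CI of k/6 |
|---|---|---|---|
| 0 | 0/6 = 0% | 0/6 = 0% | 0 to 45.9% |
| 1 | 0/6 = 0% | 1/6 = 16.7% | 0.4 to 64.1% |
| 2 | 0/6 = 0% | 2/6 = 33.3% | 4.3 to 77.7% |
| 3 | 0/6 = 0% | 3/6 = 50.0% | 11.8 to 88.2% |

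With k = 1 the onset table reads 1/6 at 10 mg and 0/6 at 70 mg. With worsening counted it reads 1/6 at both. The intervals are wide, so a shift of one patient lies well within chance. It matters for what the table displays, not for any formal test.

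**Step 3: events before Day 1.** Protocol 9.1 records events from consent. SAP 8.6 explains a period only as a dose level. The rule is therefore silent on an event that begins in screening and worsens on treatment. The text does not say whether such an event is counted, or where.

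**The case against.** The case against giving this much weight is strong in several places.

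**No case is shown.** The effect needs at least one event that worsened across levels and stayed in one record. The documents report none. Protocol 1.2 says there were no serious adverse events and no premature treatment discontinuations due to adverse events. Protocol 7.1 requires treatment to stop for grade 3 diarrhoea, so an event of that kind would have surfaced whatever the table showed. This stands. What remains possible is a milder rise, such as grade 1 to grade 2, which those statements do not exclude.

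**The information may be visible elsewhere.** With six patients, a reader can go through every event in the by-patient display. This stands in part: the display reveals worsening at a later dose only if grade changes are dated, which the unredacted text does not require.

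**The table did not drive the dose.** A reader might infer that the rule distorted the choice of 70 mg. The documents do not support that. SAP 7.1.1 makes pAkt in B cells the primary parameter for selecting the dose and lists safety among other variables. Protocol 3.2.2 justifies 70 mg by pathway suppression. Escalation relied on a continuous safety review (SAP 2.2.1), and no formal comparison of event rates between doses is visible. Tolerability is still a stated basis in Protocol 3.1.2, so the table is not irrelevant.

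**The net bias is unknown.** A reader might also infer that 70 mg must look better tolerated than it was. Dose and time rise together here, so the same onset rule charges late background events and delayed effects of lower doses to 70 mg. Only the shift for worsening single-record events has a fixed direction.

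**Redaction.** A worsening rule or a severity table may exist in text that is not available. The point is therefore limited to the visible text.

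**Conclusion.** The point holds as a modest reporting gap. The counting rule, as written in both documents, can leave a worsening event out of the higher dose's row, by 16.7 percentage points per affected patient in the relevant row. This rests on three assumptions: the worsening event is one record with its original start date, the patient has no other onset under that row in the later period, and no redacted or separate specification already deals with worsening.

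It does not show that the Part I table is wrong, that the conclusion on tolerability is unsound, or that dose selection was affected. The number of such events cannot be determined from the documents, and it may be zero. The change is worth making because it is cheap, adds to what is shown without removing anything, and would confirm or qualify a statement made for each dose level on a primary Part I objective.

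**What to change.** Change the tabulation only. Part I is complete, so this would be a supplementary output, labelled as added after the fact.

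1. In Part I SAP 8.6, keep the onset rule for an event that continues at the same or a lower grade.
2. Add that an event whose CTCAE grade increases in a later dose period is also counted in that period, at its highest grade there.
3. State that an event present before Day 1 that worsens on treatment is counted in the period of worsening.
4. Add a table of maximum grade by dose level, and state whether a grade increase was stored as a new record or within the existing one. If grade changes were not dated, say so as a limit of the table.
5. Show the onset-based table beside it.

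The cost is a few sentences and one further table for six patients. There are two small downsides. An event may appear under two dose levels, so the period counts no longer add up to the number of events. Worsening that reflects time or cumulative exposure will be placed at the higher dose, because a forced titration cannot separate the two. Showing both tables makes that visible.
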